6.11.4.1. Leukocytes (WBC) and Platelets

Further analyses will be conducted for total leukocytes, neutrophils, platelets, lymphocytes, monocytes, eosinophils, and basophils. Unless otherwise specified, neutrophils will be summarized as absolute neutrophils (derived by adding segmented neutrophils and band neutrophils).

Shift table will be produced showing the number and percentage of patients shifting from baseline to a minimum postbaseline result in each relevant category by treatment groups for study Periods 2 and 3, respectively:

- Scheduled visits, unscheduled visits, and repeat measurements will be included.
- Baseline is defined as the minimum result during the defined baseline period or baseline.
- Use the minimum non-missing postbaseline value within each study period.
- The parameters and categories are:
 - Leukocytes: $\geq 1 \times \text{LLN}$ (Normal), $< \text{LLN}$ to $\geq 3.0 \times 10^9/\text{L}$ (Grade 1), $< 3.0 \times 10^9/\text{L}$ to $\geq 2.0 \times 10^9/\text{L}$ (Grade 2), $< 2.0 \times 10^9/\text{L}$ to $\geq 1.0 \times 10^9/\text{L}$ (Grade 3), and $< 1.0 \times 10^9/\text{L}$ (Grade 4).
 - Neutrophils: $\geq 1 \times \text{LLN}$ (Normal), $< \text{LLN}$ to $\geq 1.5 \times 10^9/\text{L}$ (Grade 1), $< 1.5 \times 10^9/\text{L}$ to $\geq 1.0 \times 10^9/\text{L}$ (Grade 2), $< 1.0 \times 10^9/\text{L}$ to $\geq 0.5 \times 10^9/\text{L}$ (Grade 3), and $< 0.5 \times 10^9/\text{L}$ (Grade 4)
 - Platelets: $\geq 1 \times \text{LLN}$ (Normal), $< \text{LLN}$ to $\geq 75.0 \times 10^9/\text{L}$ (Grade 1), $< 75.0 \times 10^9/\text{L}$ to $\geq 50.0 \times 10^9/\text{L}$ (Grade 2), $< 50.0 \times 10^9/\text{L}$ to $\geq 25.0 \times 10^9/\text{L}$ (Grade 3), and $< 25.0 \times 10^9/\text{L}$ (Grade 4).
 - Lymphocytes: $\geq 1 \times \text{LLN}$ (Normal), $< \text{LLN}$ to $\geq 0.8 \times 10^9/\text{L}$ (Grade 1), $< 0.8 \times 10^9/\text{L}$ to $\geq 0.5 \times 10^9/\text{L}$ (Grade 2), $< 0.5 \times 10^9/\text{L}$ to $\geq 0.2 \times 10^9/\text{L}$ (Grade 3), and $< 0.2 \times 10^9/\text{L}$ (Grade 4).
- The above LLNs are defined as:
 - Leukocytes: $\text{LLN} = 4.0 \times 10^9/\text{L}$
 - Neutrophils: $\text{LLN} = 2.0 \times 10^9/\text{L}$
 - Platelets: $\text{LLN} = 150 \times 10^9/\text{L}$
 - Lymphocytes: $\text{LLN} = 1.1 \times 10^9/\text{L}$
- With additional categories:
 - Decreased; postbaseline category $<$ baseline category
 - Increased; postbaseline category $>$ baseline category
 - Same; postbaseline category = baseline category.

The change from minimum baseline to minimum postbaseline result for each of these leukocytes and platelets will be summarized graphically using a box plot for Periods 2 and 3, respectively.

6.11.4.2. Neutrophil Follow-Up

Neutrophil counts will be followed throughout the study. The neutrophil follow-up analysis will be conducted on the Neutrophil Follow-Up Population defined as patients who have an absolute neutrophil count < 1500 cells/ μL (SI units: $< 1.5 \times 10^9/\text{L}$) at the last scheduled visit or early termination visit prior to entering Period 4 and less than the patient's baseline absolute neutrophil count (that is, prior to first injection at Week 0).

Neutrophil clinical recovery is defined as an absolute neutrophil count ≥ 1500 cells/ μL (SI units: $\geq 1.5 \times 10^9/\text{L}$) or greater than or equal to a patient's minimum absolute neutrophil count prior to first study drug injection at Week 0. If a patient's neutrophil count has not recovered within 12 weeks after entering the follow-up period (Visit 802), the investigator will determine the appropriate management of the patient and the appropriate timing of additional contact(s).

The number and percentage of patients achieving neutrophil clinical recovery will be presented by treatment groups and week interval for the Neutrophil Follow-Up Population for Period 4. The number and percentage of patients with an absolute neutrophil cell count that is at least 25%,

50%, 75%, or 100% of the patient's baseline absolute neutrophil count (that is, prior to first injection at Week 0), irrespective of absolute neutrophil minimum, will be included in the summary.

6.11.5. Vital Signs and Other Physical Findings

Analyses will be conducted on vital signs and physical characteristics including systolic blood pressure (mmHg), diastolic blood pressure (mmHg), pulse (bpm), weight (kg), BMI (kg/m²).

Change from baseline to last observation for vital signs and physical characteristics will be summarized for patients who have both baseline and at least one postbaseline result, for Periods 2, and 3, respectively:

- The scheduled visits/measurements will be included. The unscheduled visits and the repeat measurements will be excluded.
- For the Safety Population for Period 2, the comparisons between treatment groups will be conducted using an ANCOVA with treatment groups and baseline value in the model.
- Data will be analyzed based on original scale.

For vital signs and physical characteristics, the observed values at each visit (starting at baseline) and change from baseline to each scheduled visit, respectively, will be displayed in box plots for patients who have both a baseline and at least one postbaseline result. These box plots will be used to evaluate trends over time and to assess a potential impact of outliers on central tendency summaries.

- The scheduled visits/measurements will be included. The unscheduled visits and the repeat measurements will be excluded.
- The following summary statistics will be included as a table below the box plot: number of patients with a baseline and at least one postbaseline result, mean, standard deviation, minimum, Q1, median, Q3, and maximum.
- Data will be summarized based on original scale.

To assess the effect of administration of study drug on vital signs (blood pressures and pulse rate) among patients, at weeks 0, and 16, vital signs will be measured before the first injection and 1 hour after the injection. The box plots will be produced for pre-dose and post-dose vital signs at Week 0 (Visit 2), and Week 16 (Visit 8).

The number and percentage of patients with treatment-emergent or follow-up emergent high or low vital sign and weight at any time for Periods 2, 3, and 4 (for vital signs only in Period 4), respectively, will be summarized. The comparisons between and among treatment groups will be conducted using Fisher's exact test for the Safety Population for Period 2.

- [Table RHCH.6.8](#) defines the high and low baseline values as well as the limits that are specified as treatment-emergent and follow-up emergent. Note that weight does not have an abnormal baseline; therefore, the treatment-emergent and follow-up emergent values are determined by change from baseline.
- All postbaseline scheduled, unscheduled and repeated measurements will be included.

- To assess increases, change from the maximum value during the baseline period or baseline to the maximum value during each study period will be used.
- To assess decreases, change from the minimum value during the baseline period or baseline to the minimum value during each study period will be used.
- For treatment-emergent high and low:
 - A treatment-emergent **high** result is defined as a change from a value less than or equal to the high limit at baseline to a value greater than the high limit at any time that meets the specified change criteria during the treatment period.
 - A treatment-emergent **low** result is defined as a change from a value greater than or equal to the low limit at baseline to a value less than the low limit at any time that meets the specified change criteria during the treatment period.
- For follow-up emergent high and low:
 - A follow-up emergent **high** result is defined as a change from a value less than or equal to the high limit at baseline to a value greater than the high limit at any time that meets the specified change criteria during the follow-up period.
 - A follow-up emergent **low** result is defined as a change from a value greater than or equal to the low limit at baseline to a value less than the low limit at any time that meets the specified change criteria during the follow-up period.

Table RHCH.6.8. Categorical Criteria for Abnormal Treatment-Emergent Blood Pressures and Pulse Measurement, and Categorical Criteria for Weight Changes for Adults

Parameter	Low	High
Systolic BP (mm Hg) ^a (supine or sitting – forearm at heart level)	≤90 and decrease from baseline ≥20	≥140 and increase from baseline ≥20
Diastolic BP (mm Hg) ^a (supine or sitting – forearm at heart level)	≤50 and decrease from baseline ≥10	≥90 and increase from baseline ≥10
Pulse (bpm) ^a (supine or sitting)	<50 and decrease from baseline ≥15	>100 and increase from baseline ≥15
Weight (kg)	(Loss) decrease from baseline ≥7%	(Gain) increase from baseline ≥7%

Abbreviations: BP = blood pressure; bpm = beats per minute; kg = kilogram; mm Hg = millimeters of mercury.

^a Baseline abnormal values are defined by the value presented.

6.11.6. Quick Inventory of Depressive Symptomatology–Self Report 16 Items (QIDS-SR16)

The QIDS-SR16 is a self-administered 16-item instrument intended to assess the existence and severity of symptoms of depression as listed in the American Psychiatric Association's (APA's) *Diagnostic and Statistical Manual of Mental Disorders, 4th Edition (DSM-IV)* (APA 1994). The QIDS-SR16 scale is used to assess the potential impact of treatment on new onset or changes in depression, thoughts of death, and/or suicidal ideation severity. A patient is asked to consider each statement as it relates to the way they have felt for the past 7 days. There is a 4-point scale for each item ranging from 0 to 3. The 16 items corresponding to 9 depression domains are

summed to give a single score ranging from 0 to 27, with higher scores denoting greater symptom severity. Additional information and the QIDS-SR16 questions may be found at the University of Pittsburgh IDS/QIDS resource page (<http://www.ids-qids.org/>).

The 9 domains assessed by the instrument are defined as:

- 1) Sleep disturbance (initial, middle, and late insomnia or hypersomnia): the highest score recorded for the four sleep items: #1 (falling asleep), #2 (sleep during the night), #3 (waking up too early) and #4 (sleeping too much). Domain is missing if all items are missing.
- 2) Sad mood: Item #5 (feeling sad). Domain is missing if the item is missing.
- 3) Decrease/increase in appetite/weight: the highest score recorded for the appetite/weight items: #6 (decreased appetite), #7 (increased appetite), #8 (decreased weight within the last two weeks), and #9 (increased weight within the last two weeks). Domain is missing if all items are missing or not applicable.
- 4) Concentration: Item #10 (concentration / decision making). Domain is missing if the item is missing.
- 5) Self-criticism: Item #11 (view of myself). Domain is missing if the item is missing.
- 6) Suicidal ideation: Item #12 (thoughts of death or suicide). Domain is missing if the item is missing.
- 7) Interest: Item #13 (general interest). Domain is missing if the item is missing.
- 8) Energy/fatigue: Item #14 (energy level). Domain is missing if the item is missing.
- 9) Psychomotor agitation/retardation: the highest score recorded for the two psychomotor items: #15 (feeling slowed down) and #16 (feeling restless). Domain is missing if all items are missing.

The QIDS-SR16 total score is the sum of the above domain scores. The total score will be missing if any domain score is missing. The QIDS-SR16 total scores are categorized as: None (no depression) (0 – 5), Mild (6 – 10), Moderate (11 – 15), Severe (16 – 20) and Very severe (21 – 27).

For both Period 2 and 3 QIDS-SR16 analyses, baseline is defined as the last non-missing assessment recorded on or prior to the date of first injection of study treatment at Week 0 (Visit 2), as for QoL measures. In most cases, this will be the measure recorded at Week 0 (Visit 2).

Summaries will be done by treatment groups for Safety Population in Period 2 and Extended Treatment Period Population in Period 3, respectively.

The following summaries will be produced for QIDS-SR16 total score category:

- The number and percentage of patients falling into each QIDS-SR16 total score category at each scheduled visit.
- Shift from maximum baseline to each postbaseline visit in QIDS-SR16 total score category.

- The number and percentage of patients falling into the following categories based upon the maximum postbaseline QIDS-SR16 total score:
 - Improved; maximum postbaseline category < maximum baseline category.
 - Worsened; maximum postbaseline category > maximum baseline category.
 - Same; maximum postbaseline category = maximum baseline category.

In addition, the number and percentage of patients falling into the following groups based upon the maximum postbaseline QIDS-SR16 item 12 (Thoughts of Death or Suicide) score will be summarized:

- Improved; maximum postbaseline item 12 score < maximum baseline item 12 score.
- Worsened; maximum postbaseline item 12 score > maximum baseline item 12 score.
- Same; maximum postbaseline item 12 score = maximum baseline item 12 score.

6.11.7. Columbia-Suicide Severity Rating Scale (C-SSRS)

The C-SSRS is an assessment tool that evaluates suicidal ideation and behavior. Information on the C-SSRS scale can be found through the following link: <http://www.cssrs.columbia.edu>.

Specifically, the following outcomes are C-SSRS categories and have binary responses (yes/no).

Category 1 – Wish to be Dead

Category 2 – Non-specific Active Suicidal Thoughts

Category 3 – Active Suicidal Ideation with Any Methods (Not Plan) without Intent to Act

Category 4 – Active Suicidal Ideation with Some Intent to Act, without Specific Plan

Category 5 – Active Suicidal Ideation with Specific Plan and Intent

Category 6 – Preparatory Acts or Behavior

Category 7 – Aborted Attempt

Category 8 – Interrupted Attempt

Category 9 – Actual Attempt (non-fatal)

Category 10 – Completed Suicide.

Self-injurious behavior without suicidal intent is also a C-SSRS outcome (although not suicide-related) and has a binary response (yes/no).

Composite endpoints based on the above categories are defined below.

- **Suicidal ideation:** answered ‘yes’ to any one of Categories 1-5 questions.
- **Suicidal behavior:** answered ‘yes’ to any one of Categories 6-10 questions.
- **Suicidal ideation or behavior:** answered ‘yes’ to any one of Categories 1-10 questions.

C-SSRS will be listed by patient and visit using Spotfire. Only patients that show suicidal ideation/behavior or self-injurious behavior without suicidal intent will be displayed. However, if a patient reported any suicidal ideation/ behavior or self-injurious behavior without suicidal intent at any time point then all their ideation and behavior will be displayed, even if not positive. Note, missing data should not be imputed.

The Self-Harm Supplement Form is a one-question form that is completed, at any visit, including baseline visit, that asks for the number of suicidal behaviors, possible suicidal behaviors or

nonsuicidal self-injurious behaviors the patient has experienced since the last assessment. For each unique event identified, a questionnaire (Self-Harm Follow-up Form) which collects supplemental information on the self-injurious behavior is to be completed. The Self-Harm data will be listed by patient and visit if number of events on Self-Harm Supplement Form is not zero in the CRF '*Self Harm Questionnaire Supplement.*'

6.11.8. Immunogenicity

6.11.8.1. Definitions and Terms

The following sample- and patient-related definitions and parameters will be used to describe the immunogenicity data.

6.11.8.1.1. Sample Category Definitions

Samples are classified into the following categories:

- **Unevaluable sample:** Sample could not be tested for ADA due to sample loss, mishandling, or errors in collection, processing, storage, and so on.
- **Anti-drug antibody (ADA) Positive sample:** The presences of ADA is detected and confirmed. The samples are reported as positive. If the sample is positive, a titer value is reported.
- **Neutralizing anti-drug antibody (NAb) Positive sample:** NAb are reported as detected.
- **ADA Negative sample:** The presence of ADA is not detected and the assay drug tolerance level is not exceeded.
- **NAb Negative sample:** The presence of NAb is not detected and the assay drug tolerance level is not exceeded.
- **ADA/NAb Inconclusive sample:** when ADA/NAb is not detected in a sample but drug is present in the same sample at a level that can cause interference in the ADA/NAb detection method, then the negative ADA/NAb result cannot be confirmed and the sample should be considered inconclusive.
 - Confirmation of a negative ADA or NAb result was based on ixekizumab concentrations.

6.11.8.1.2. Patient Category Definitions

The following categories are applied to patients based on the classification of their samples:

- **Unevaluable patient:** a) a patient with no evaluable baseline sample and/or no evaluable postbaseline samples; b) a patient with an evaluable baseline sample but no evaluable postbaseline sample; c) a patient with no evaluable baseline sample, but whose evaluable postbaseline values are all ADA positive or a mix of positive and negative. (Note: If all postbaseline samples are negative, the patient is considered 'evaluable' and will be classified as ADA-negative.)

- **Evaluable patient:** a) Patient with an evaluable baseline sample and at least 1 evaluable postbaseline sample (that is, sample after administration of study drug); b) patient with no evaluable baseline sample whose evaluable postbaseline samples are all ADA negative.

6.11.8.1.3. Definitions for Clinical Interpretation of Assay Results

- **Baseline:** For immunogenicity analyses during Period 2, baseline is the last nonmissing observation on, or prior to, the date of the first injection of study treatment (Week 0). Unless otherwise specified, the baseline for Period 3 is defined as the last non-missing observation on, or prior to, the date of first injection of ixekizumab. For patients originally randomized to ixekizumab during Period 2, baseline is the last non-missing observation on, or prior to, the date of the first injection of study treatment for Period 2 (Week 0). For patients who are not originally randomized to ixekizumab in Period 2, baseline is the last non-missing observation on, or prior to, the date of the first injection of ixekizumab. See [Table RHCH.6.9](#) for further details.

Table RHCH.6.9. Baseline Definition for Immunogenicity Analyses for Extended Treatment Period

Treatment Assignment for Blinded Treatment Dosing Period (Period 2)	Treatment Assignment for Extended Treatment Period (Period 3)	Baseline for Extended Treatment Period Analysis ^a
Ixekizumab	Ixekizumab	Week 0
Placebo	Ixekizumab	Week 16

^a Last non-missing observation on, or prior to, the date of the first injection of study treatment at the defined week.

- **Baseline ADA positive (preexisting antibody) patient:** ADA detected in a sample collected at baseline.
- **Baseline ADA-negative patient:** ADA is not detected in a sample collected at baseline.
- **TE-ADA positive patient:** a) a patient with a ≥ 4 -fold increase over a positive baseline antibody titer (Tier 3); or b) for a negative baseline titer, a patient with an increase from the baseline to a level of $\geq 1:10$.
- **TE-ADA inconclusive patient:** A patient without a TE-ADA positive sample and with at least one sample for which drug levels may interfere with the ADA assay.
- **TE-ADA negative patient:** A patient who is evaluable for TE-ADA and is not either TE-ADA positive or TE-ADA inconclusive.
- **Incidence of TE-ADA:** Patients with TE-ADA as a proportion of the evaluable patient population during the treatment period. This excludes unevaluable patients.

All ADA positive samples will be evaluated for NAb. Definitions for NAb patient status will be defined as follows:

- **NAb-positive patient:** A patient where a NAb positive result is detected for ≥ 1 TE-ADA positive samples.
- **NAb-inconclusive patient:** A patient without a NAb positive sample and with at least one sample for which drug levels may interfere with the NAb assay.
- **NAb-negative patient:** A patient who is evaluable for NAb and is not either NAb positive sample or NAb inconclusive.

Please see the LY2439821 PSAP v8 section 5.6.4.1.3 (or most current version) for details on the definitions for clinical interpretation of assay results.

6.11.8.2. Immunogenicity Analyses

Immunogenicity evaluable patients will be identified as TE-ADA positive, TE-ADA negative, or TE-ADA inconclusive, according to the definitions provided in Section 6.11.8.1.2 and further grouped into TE-ADA status groups and time-varying TE-ADA status groups:

TE-ADA Status Groups:

- TE-ADA status (positive, negative, or inconclusive);
- NAb status (positive, negative, or inconclusive) for TE-ADA positive patients; and
- TE-ADA titer groups for TE-ADA positive patients:
 - Low Titer: TE-ADA titer value (LOCF) $< 1:160$;
 - Moderate Titer: TE-ADA titer value (LOCF) $\geq 1:160$ and $< 1:1,280$; and
 - High Titer: TE-ADA titer value (LOCF) $\geq 1:1,280$.

Time-Varying TE-ADA Status Groups:

Individual ADA samples will be ascribed into 3 different dichotomous variables as explained in Table RHCH.6.10. Each variable has possible values of a “greater-TE-ADA status” or a “lesser-TE-ADA status,” in the sense that the level of TE-ADA detected in the greater-TE-ADA category is higher than in the lesser-TE-ADA category.

Table RHCH.6.10. TE-ADA Status Dichotomous Variables for AE Analysis

TE-ADA Status Dichotomous Variable	Greater-TE-ADA Status	Lesser-TE-ADA Status
TE-ADA positive	TE-ADA positive	not TE-ADA positive
TE-ADA moderate-to-high	TE-ADA positive with moderate titer or high titer	not TE-ADA positive, or TE-ADA positive with low titer
TE-ADA high status	TE-ADA positive with high titer	not TE-ADA positive, or TE-ADA positive with low or moderate titer

Abbreviations: AE = adverse event; TE-ADA = treatment-emergent anti-drug antibody.

Note: For purpose of this analysis, TE-ADA Inconclusive is taken to be “not TE-ADA positive.”

Note: A TE-ADA low is defined as a TE-ADA positive with a titer value $< 1:160$; a TE-ADA moderate is defined as a TE-ADA positive with a titer value $\geq 1:160$ and $< 1:1,280$; and a TE-ADA high is defined as a TE-ADA positive with a titer value $\geq 1:1,280$.

For each TE-ADA status dichotomous variable, a time-varying TE-ADA status will be computed. At time t , the TE-ADA status is taken to be the highest of the TE-ADA values

bracketing time t . More formally, the TE-ADA status at time t is given by the greater of (a) the TE-ADA status at the most-recent postbaseline measurement prior to t , and (b) the TE-ADA status at the first TE-ADA postbaseline measurement at or after time t . In this computation, “greater” is given by the greater-TE-ADA status of [Table RHCH.6.10](#). If there is no value satisfying criterion (a), then the value (b) is used. Similarly, if there is no value (b), then the value (a) is used.

For each TE-ADA status dichotomous variable, patients will be categorized according to whether they were (i) always in lesser-TE-ADA status postbaseline or (ii) at some point postbaseline, were in greater-TE-ADA status.

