6.11.8.2.2. Analyses of ADA Effects on Efficacy

Efficacy analyses for Period 2 and Period 3 will be conducted on all evaluable patients within the ITT Population and Extended Treatment Period Population.

The ASAS40, ASAS20, ASDAS inactive disease and ASDAS < 2.1 at week 16 with NRI will be summarized by the TE-ADA status groups as described in Section 6.11.8.2.

A logistic regression model with treatment group, TE-ADA status group (excluding patients in the TE-ADA inconclusive category for TE-ADA, excluding TE-ADA positive and co-occurring NAb inconclusive subgroups for NAb), and the interaction of treatment group-by-TE-ADA status group included as factors will be used to test the interaction of treatment group-by-TE-ADA status group for ITT Population during Period 2. The p-value associated with the interaction term will be used to assess if the treatment groups effect is consistent across the TE-ADA status group. When the interaction term is statistically significant, the association between responder status and treatment depends, in some manner, on the TE-ADA status group. The interaction will be tested at the 10% significance level. Treatment differences will be evaluated within each subgroup using Fisher's exact test regardless of whether the interaction is statistically significant.

Response rates for ASAS40, ASAS20, ASDAS inactive disease and ASDAS < 2.1 at Week 16 will be provided and compared among the TE-ADA status (and TE-ADA tiers) and NAb status groups for the ITT Population who were treated with ixekizumab.

Descriptive statistics for ASAS40 and ASAS20 at Week 52 based on the TE-ADA status (and TE-ADA tiers) and NAb status group will be provided for the Extended Treatment Period Population. No inferential statistics will be performed.

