6.11.8.2.3. Analyses of Treatment-Emergent ADA on Specific Adverse Events

The analyses of TE-ADA effects on safety will be conducted on all evaluable patients within the defined Safety Population for Blinded Treatment Dosing Period (Period 2) and Combined Blinded Treatment Dosing and Extended Treatment Periods (Combined Periods 2 and 3).

Baseline definition for immunogenicity analyses for the Combined Treatment Period is the same as [Table RHCH.6.9](#).

AESIs of allergic reaction/hypersensitivity (anaphylaxis and non-anaphylaxis) and of injection-site reactions will be included in an assessment of AE to TE-ADA over time. Timing of an AE will be taken to be the reported AE start date.

For each TE-ADA status dichotomous variable (as defined in [Table RHCH.6.10](#)), patients will be categorized according to whether they were (i) always in lesser-TE-ADA status postbaseline or (ii) at some point postbaseline, were in greater-TE-ADA status. For each AESI, within the time-varying TE-ADA status groups, a summary will be provided of the number of patients who

had no event, events only while in lesser-TE-ADA status for group (i), or – for group (ii) – at least one event while in greater-TE-ADA status.

Additionally, summaries will be provided of the total number of AESI events (with unique start dates) by time-varying TE-ADA status groups at the event date. The summaries will aggregate time respectively in greater-TE-ADA status and in lesser-TE-ADA status, along with the event rates (rates per 100 patient-years) relative to those aggregate times.

By-patient listings will be provided of patients with TE-ADA who experience a treatment-emergent allergic reaction/hypersensitivity reaction or an injection site reaction.

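### The antibody-by-AE tables pool TE-ADA inconclusive time with confirmed-negative time, which can dilute a link to allergic and injection-site events; it should be shown as a third status.

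*SAP*

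**What the plan says.** SAP Section 6.11.8.1.1 defines an inconclusive sample as one where no antibody is detected but drug is present at an interfering level; "then the negative ADA/NAb result cannot be confirmed and the sample should be considered inconclusive". Section 6.11.8.1.3 carries this to the patient level. An inconclusive patient is "A patient without a TE-ADA positive sample and with at least one sample for which drug levels may interfere with the ADA assay", and a TE-ADA negative patient is an evaluable patient who is neither positive nor inconclusive.

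For the AE analysis, Section 6.11.8.2 sets up three two-level variables in Table RHCH.6.10, and the note under the table says "For purpose of this analysis, TE-ADA Inconclusive is taken to be" not TE-ADA positive. Status between samples follows a bracketing rule: "the TE-ADA status at time t is given by the greater of" the last earlier post-baseline result and the next one.

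Section 6.11.8.2.3 uses these variables: "AESIs of allergic reaction/hypersensitivity (anaphylaxis and non-anaphylaxis) and of injection-site reactions will be included". Patients and events are counted by status, and rates per 100 patient-years are formed: "The summaries will aggregate time respectively in greater-TE-ADA status and in lesser-TE-ADA status". No AE table separates inconclusive time.

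The efficacy interaction model in Section 6.11.8.2.2 handles the same category differently, "excluding patients in the TE-ADA inconclusive category for TE-ADA". Protocol Section 10.3.11 describes the safety comparison as antibody-positive patients with these events against patients with the same kinds of event who stay antibody negative.

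**The concern.** The reference column of the AE tables mixes two kinds of time: time bracketed by confirmed negatives, and time for which the assay could not rule antibodies out. The SAP's own definitions keep these apart. If antibodies do raise the rate of hypersensitivity or injection-site reactions, and some inconclusive time is truly positive, events from that time are counted against the reference. The reference rate rises and the two columns look more alike. For a safety question, that error leans toward reassurance. A reader of the AE tables would also be unable to see how much reference time was unconfirmed. Neither document explains why safety and efficacy treat the category differently.

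**Working it through.** The documents state no figure on this point, so there is none to reproduce.

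**1. Which time is pooled.** I applied the bracketing rule to the scheduled post-baseline antibody samples in the protocol Schedule of Activities: Weeks 1, 2, 4, 8, 12, 16, 24, 36 and 52. Take a hypothetical patient who is truly positive throughout Weeks 0 to 52 and reads positive at every visit not listed as inconclusive:

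- One inconclusive sample at any visit from Week 2 on: 0 of 52 weeks move to lesser status, because a neighbouring positive sample covers both sides.
- One inconclusive sample at Week 1: 1 week moves, because no earlier post-baseline sample exists.
- Two in a row: the interval between them moves. Weeks 8 and 12: 12 − 8 = 4 weeks. Weeks 24 and 36: 36 − 24 = 12 weeks. Weeks 36 and 52: 52 − 36 = 16 weeks.
- Inconclusive at Weeks 1 to 16, positive afterwards: 16 weeks move and 52 − 16 = 36 remain in greater status.
- Inconclusive at every visit: all 52 weeks move.

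Isolated inconclusive samples therefore cost almost nothing. The exposure comes from runs of them, chiefly in Period 3 where samples are 8 to 16 weeks apart, and from patients who never have a positive sample.

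**2. How much dilution could follow.** Inputs, none of them in the documents and all assumed:

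- f: share of lesser-status time that is inconclusive
- q: share of that inconclusive time that is truly positive
- R: true event-rate ratio, positive against not positive

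The masked-positive share of reference time is m = f × q. With a rate of λ in truly non-positive time and Rλ in truly positive time, the reference rate is λ(1 − m) + Rλm = λ[1 + m(R − 1)]. If greater-status time is all truly positive,

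observed ratio = R / [1 + m(R − 1)].

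| f | q | m | R = 3 | R = 2 |
|---|---|---|---|---|
| 0.10 | 0.10 | 0.01 | 3/1.02 = 2.94 | 2/1.01 = 1.98 |
| 0.20 | 0.25 | 0.05 | 3/1.10 = 2.73 | 2/1.05 = 1.90 |
| 0.40 | 0.50 | 0.20 | 3/1.40 = 2.14 | 2/1.20 = 1.67 |
| 0.40 | 1.00 | 0.40 | 3/1.80 = 1.67 | 2/1.40 = 1.43 |

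If q = 0 or R = 1, the observed ratio equals R and there is no dilution. The ratio is only a scale for the effect: Section 6.11.8.2.3 plans rates by status, not a ratio or a test. The formula is written for the first of the three variables (TE-ADA positive or not).

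**3. After the change.** With inconclusive time in its own column, m from this source is 0 and the expected ratio returns to R, before any error from the bracketing rule itself.

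**The case against.** The rule is explicit and pre-specified, and it affects a descriptive table. Several points in its favour stand:

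- Drug being present does not by itself make a sample inconclusive. Protocol Section 9.4.4 describes an assay designed to find antibodies with drug present. Sections 9.5 and 2 match antibody samples to PK samples drawn before injection, so samples at dosing visits are near trough (Weeks 1 and 2 are not).
- The bracketing rule already sends time beside any positive sample to greater status.
- The SAP label is not TE-ADA positive, which makes no claim that antibodies are absent. For the moderate-to-high variable, lesser status is "not TE-ADA positive, or TE-ADA positive with low titer", and the high variable adds moderate titers.
- Section 6.11.8.2.1 tabulates patients by TE-ADA status group, inconclusive included, and lists inconclusive results with drug concentration. Section 6.11.8.2.2 also summarises response by those groups, so exclusion applies to the interaction model and not to all efficacy output.
- Removing inconclusive time outright could delete hypersensitivity events, including those whose event-triggered sample was inconclusive, and could discard intervals with one positive and one inconclusive end.

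These points limit the size of the problem and rule out simple exclusion. They do not explain why an unconfirmable result belongs in the reference column with no display of its share: the patient-level frequencies and the listing are not tied to AE rates. The SAP refers to a program safety analysis plan for interpretation details; that document is not available here and may give a reason.

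**Conclusion.** The point holds in a limited form. Time with no positive bracketing sample and at least one inconclusive sample is pooled with confirmed-negative time. That is at odds with SAP Sections 6.11.8.1.1 and 6.11.8.1.3 and with the comparator in protocol Section 10.3.11, and it differs from the efficacy interaction model. Dilution is possible, conditional and of unknown size. It requires that some inconclusive time be truly positive and that antibodies raise event rates. The figures of 2.73 and 2.14 for a true ratio of 3 rest on assumed masked shares of 5% and 20%.

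A reader might infer three stronger things, and the documents support none of them. The first is that all unmeasurable time is treated as antibody-free; the bracketing rule and the composition of lesser status say otherwise. The second is that any antibody effect must be diluted; there is none if q = 0. The third is that inconclusive samples must be common because protocol Section 5.4 expects steady state by Week 16; no inconclusive rate or drug tolerance level is given.

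This is an inexpensive improvement to a descriptive safety analysis. It has no bearing on the primary or major secondary endpoints.

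**What to change.** In the Section 6.11.8.2.3 tables, add inconclusive as a third status, with its own patients, events and patient-years, for time where neither bracketing sample is positive and at least one is inconclusive. Keep the present rule for time next to a positive sample, and delete no events. Report two sensitivity codings beside it: the current one (inconclusive as lesser status) and one that counts inconclusive as positive. These are the extremes of classification; they need not enclose the true rate ratio, since that also depends on where the events fall. Reword the note to Table RHCH.6.10 to match Section 6.11.8.1.3 and protocol Section 10.3.11, or state why AE handling differs.

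The cost is an edit to one SAP note, a derivation change and an extra column, with no new data. The reference group loses some patient time, so its rates will be somewhat less precise.
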